4.4.1 Statistical methods for the main objective

Estimate Phased RFA 12 months success rate

Rational: Previous studies have demonstrated that Phased RFA with the predicate platinum electrode catheter, PVAC, effectively isolates PVs with an average chronic efficacy of 74% with average follow up of 10 months. The Phased RFA literature meta-analysis published by Andrade, et al (19) reported comparable chronic success (6 months FU) was reported as 81.4% and 54.1% for paroxysmal and persistent AF, respectively.

The clinical effectiveness of PVAC GOLD catheter has yet to be estimated in PMR observational studies to establish if prospective interventional studies outcome is reproducible in daily clinical practice.

Main observational criteria: Success rate estimated as the time to first AF recurrence and/or left Afl and/or AT event from the index procedure. Data about AF events will be collected since the index procedure, including 90 days of the “blanking period” and closes at 12 months FU. If no AF/left Afl and/or events occur during the entire follow up period, 12 (+2) months, the case is considered to be “event-free”.

End point definition:

1. AF pharmacological and/or electrical CV
2. AF and or left Afl more the 30 sec on ECG/EGM
3. AF less than 30 sec in combination with AF symptoms
4. Re-ablations for AF
5. Ablations for left Afl or left AT

Analysis Methods: Freedom from AF recurrence at 12 months will be estimated using Kaplan-Meier methods. A point estimate at the date of 12 months FU post procedure will be presented. Standard error will be approximated using Greenwood's formula, and a two-sided 95% log-log confidence interval will be presented. Day 0 is defined at the date of index procedure. For patients with an AF recurrence, follow up time will be set to the date of recurrence. For patients without a reported AF recurrence, those patients will be censored at the last study contact date.

Limitations: Time to first AF recurrence has practical advantages as a primary endpoint, but does not accurately reflect clinically important parameters such as the frequency, type, and duration of AF recurrence and the overall AF burden. Above known, that significant percentage of patients has silent (or asymptomatic) AF and even more, the tendency to convert symptomatic form AF to asymptomatic after PVI.

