Data entered in the EBogen system is checked for completeness and accuracy of data entry, directly. By default, all fields are marked as required. However, with the exception of the first page containing the stratification and eligibility questions, the navigation in the CRF is not restricted, even if fields are missing or contain invalid data. All fields that are optional have been assigned an "NA" checkbox or a similar option to specify that this field is not available. Checking this "NA" option will disable the original data entry field to signal that the value is not available. Fields that are foreseen for specific investigations (non-mandatory investigations) are only available when the leading question has been marked "yes", or the obvious corresponding choice was made. Depending on the layout and size of the fields these conditional fields will be either disabled or made invisible until the appropriate prerequisite is fulfilled.

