### 4.3 Full Analysis Set

The *Full Analysis Set* (FAS) consists of all patients of the BAS and thereof patients with a valid 12MFU form of 12 months visit or 12 months telephone interview. The rules for valid 12MFU form are described in the chapter 7.2.3.

A documented 12MFU form includes at least:

- Date of the visit/FU and
- Vital status and
- Signed eCRF 12MFU visit or 12MFU by phone form

The FAS will be used to analyse the main objective (SAP chapter 8.1), additional objective (SAP chapter 8.2) and ancillary objectives (SAP chapter 8.3). The FAS will be analysed at the end of this study.

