# 6 Target Variables

## 6.1 Study Population

Data from all patients who are enrolled in the study (patients who meet the eligibility criteria and signed the PIC/PDRF) will be included in the analysis. If a patient exits from the study, data collected prior to the study withdrawal can be included in the analysis in compliance with PIC/PDRF unless patient requests deletion of the personal data when exit the study in compliance with local regulations.

The following parameters will be used to characterise the study population and to give an overview on the documented visits:

- Overview about patient status
  - number of patients in the All-Documented Patients Set (APS),
  - number of patients in Baseline Analysis Set (BAS),
  - number of patients in Full Analysis Set (FAS)
  - number of patients in Extended Full Analysis Set (EFAS)
- Overview about reasons for being excluded from the different analysis sets
  - Criteria for the BAS
  - Criteria for the FAS
- Number of documented patients per site (BAS)
- Number of documented patients per visit and visit period (FAS)
- Number of documented visits per patient (FAS)
- Number of documented patients by visit pattern (FAS)

A patient is defined as "documented" at a respective visit, if the FU form has a date of the visit and it is non-empty (at least one further entry) for that visit.

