### 7.2.3 Follow-up data

Only unique 12MFU form per patient will be used for analysis. If a General Follow-up visit meets the time window of the 12MFU visits (>351d after procedure), manually data review and selection will be performed. Any FU forms older than 440 days after procedure will not be used for analysis (protocol deviation). For patients with contradictory information in the eCRF the following rules are applied:

1. 12 month FU (by phone or visit) is preferred to GFU.
2. Events are always kept, even if GFUs are discarded.

The decision on patient level is given in Appendix F.

12MFU visit and 12MFU by phone results will be analysed combined, where variables were recorded in a similar manner (demographics, symptoms, hospitalization, medication). Not combinable information will be shown separately.

General FU (GFU) data will be assigned to the respective time period after first documented procedure:

- 0 to 3 months (1 day <= time between procedure and GFU <= 90 days)
- 3 to 6 months (90 days < time between procedure and GFU <= 180 days)
- 6 to 9 months (180 days < time between procedure and GFU <= 270 days)
- 9 to 12 months (270 days < time between procedure and GFU <= 351 days)

Multiple GFU per patient within one time period will be shown separately in chronological order (i.e. all first GFUs in one time period, all second GFUs in one time period and so on) as descriptive tables.

Number of GFUs per time period and time (days) until GFU during the time period (for each visit per time period) will be shown. Event rates for clinical events (history of AF, re-ablations and hospitalizations) will be calculated for 3, 6 and 9 months after discharge exactly using appropriate statistical methods.

Predefined time windows for GFU from CIP Version 2.0, Table 7.2 will not be applied.

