### 8.1.2 Methodology for analysing the main objective

Any AF re-occurrence event (Tables 5, 6 and 7) during the “blanking period” will be not be considered. “Blanking period” starts with the day of the first documented procedure and ends at exact 90 days. The first documented date of AF re-occurrence will be set as the event date. “Blanking period” for patients with additional procedure(s) at any time will not be started newly, they will be considered as “not-event free” at time of the first additional procedure.

Freedom from AF re-occurrence at 12 months will be estimated using Kaplan-Meier methods (time-to-first-event-analysis). A point estimate at the date of 12MFU post first documented procedure will be presented. Standard error will be approximated using

Greenwood's formula, and a two-sided 95% log-log confidence interval will be presented. For patients without a reported AF re-occurrence event, those patients will be censored. In this case, the right-censoring time will be set to the last study contact date. Main objective Kaplan-Meier estimation results will be displayed in percentages at 12 months (351 days) after first documented procedure. Estimated AF re-occurrence rates by month (at the end of month 3 to 11 after first documented-procedure) will be calculated and displayed as well. For group comparisons Log-Rank test will be applied. Also, Hazard ratios and 95% confidence intervals will be shown (for group comparisons, please see SAP chapter 8.6). For Kaplan-Meier estimation, numbers at risk will be displayed for reasonable points in time.

Re-occurrence of AF during 12 months (considering the "blanking period") will also be analysed via Cox proportional hazard regression model presenting hazard ratios and the corresponding 95% CI. Independent variables will be determined by Phased RFA procedure experts or physicians. Cox modelling for AF re-occurrence will be done for all pre-defined subgroups (FAS patients) where the analysis scope is the 12 month outcome (SAP chapter 8.6.1). Further Cox modelling (e.g. for multiple AF events) may be applied.

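### Patients without a reported recurrence are censored at last contact even if AF status was not recorded there, so an unanswered 12-month AF item counts as AF-free at day 351

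*SAP*

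**What the plan says.** - **Form content.** SAP 4.3 says "A documented 12MFU form includes at least" three things: the date, the vital status and a signed eCRF form. It adds: "The rules for valid 12MFU form are described in the chapter 7.2.3". SAP 7.2.3 then says "Only unique 12MFU form per patient will be used for analysis", drops forms later than day 440, and gives rules for choosing between contradictory forms. Neither section mentions the AF-history item.
- **Events.** SAP 8.1.1, Tables 4 to 6, takes recurrences from positive entries only: AF history, re-ablation, AF as visit reason, AF hospitalization, and adverse-event text. Under SAP 8.1.2 an additional procedure also ends event-free status.
- **Censoring.** For patients with no reported recurrence, SAP 8.1.2 says: "In this case, the right-censoring time will be set to the last study contact date". CIP 4.4.1 has the same rule: "those patients will be censored at the last study contact date".
- **Timing.** SAP 8.1.1 reads the estimate at day 351. CIP Table 7-2 puts the 12-month window at days 351 to 425.
- **Data entry.** CIP 7.4 marks fields as required by default, but also says "the navigation in the CRF is not restricted, even if fields are missing or contain invalid data", and gives optional fields an NA box.

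**The concern.** A censoring time in a Kaplan-Meier analysis should be the last time at which the patient was known to be free of the event. The plan uses the last time the patient was contacted. The two coincide only if AF status was established at that contact, and no rule in the plan ensures this. A blank or NA answer is handled exactly like a recorded no.

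Elsewhere the SAP does deal with missing items. SAP 8.3.1 leaves out procedures without verified block, 7.4.2 does not calculate a risk score when a component is missing, and several Appendix D comparisons require the grouping variable to be available. The Appendix D comparison by AF recurrence has no such condition.

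At stake is the main objective. The same censoring rule serves the Baseline Analysis Set, the FAS and the Extended FAS, and the error runs in one direction because a blank item cannot add an event.

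**Working it through.** The plan gives no figure for forms without an AF answer, so there is none to reproduce. The question is what the rule does, and how large the effect could be.

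**Inputs**
- S, true 12-month success: 74% (earlier studies, CIP 4.4.1), with 54.1% (persistent) and 81.4% (paroxysmal) from the meta-analysis cited there. These serve as illustrations.
- f, share of analysed patients with a 12-month form, no AF answer and no positive AF record elsewhere: not in the documents. Assumed 1, 5 and 10%.
- Form date on or after day 351, read-out at day 351.

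**Formula.** In the FAS nobody without an event is censored before day 351, so the estimate equals the share without a recorded event. Affected patients contribute 1 instead of S:

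reported = S(1 − f) + f, so overstatement = f(1 − S).

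| S | f = 1% | f = 5% | f = 10% |
|---|---|---|---|
| 81.4% | 0.2 | 0.9 | 1.9 |
| 74% | 0.3 | 1.3 | 2.6 |
| 54.1% | 0.5 | 2.3 | 4.6 |

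(percentage points; for example 0.05 × 0.26 = 0.013)

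**Effect of earlier visits.** The formula assumes that nothing was recorded about AF after the 90-day blanking period. Suppose instead that AF status was known to day 180. With a constant hazard from day 90, S(180) = 0.74^(90/261) = 0.90. Only recurrences after day 180 are missed, so the overstatement is f × (0.90 − 0.74) = 0.16f. At f = 5% that is 0.8 points instead of 1.3.

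**Simulation.** 200,000 patients, constant hazard after day 90, form dates on days 352 to 425, AF answers missing at random, true success 74.0%:

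| f | Censored at last contact | Affected patients censored at day 90 |
|---|---|---|
| 5% | 75.3% | 74.0% |
| 10% | 76.6% | 74.0% |
| 20% | 79.2% | 74.0% |

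Censoring at the last date with known AF status removes the overstatement when missingness is unrelated to recurrence.

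**Yardstick.** The stated half-width is ±3.8 points for n = 800. The plan's own inputs (20%, design effect 1.2) give 1.96 × √(1.2 × 0.2 × 0.8 / 800) = 3.0 points. At S = 74% the overstatement reaches 3.0 points only when f is about 12% (3.04 / 26).

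**The case against.** The strongest reply is that such forms should be rare. Fields are required by default, and the NA box is only for optional fields. The signature documents that the site has finished the section. CIP 7.1.2 has data reviewed for completeness and queried, missing data count as a deviation, and the phone interview follows a standard questionnaire matched to the eCRF. SAP 7.5.1 also confines evaluation to observed cases, which could be read as dropping patients whose AF status is blank.

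The controls stand as reasons to expect a small f. They do not make it zero, because entry can continue with fields missing and no passage says that a blank AF item prevents signing. The observed-cases sentence is general. It does not say whether such a patient is dropped, censored earlier or left in, while 8.1.2 gives a specific rule.

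Several stronger readings are not supported:
- **That an affected patient cannot have an event.** Positive general follow-up, hospitalization, adverse-event and re-ablation records still count.
- **That patients who die are carried AF-free past death.** SAP 4.3 asks for vital status without requiring the patient to be alive, and no passage censors at death. But deaths are reported on the Exit form, and nothing says that last contact runs beyond death. This is a gap to close, not a shown error.
- **That SAP 6.1 is at fault.** It treats a visit as documented "if the FU form has a date of the visit and it is non-empty (at least one further entry) for that visit", but that serves visit counts, not the endpoint.

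**Conclusion.** The point holds as a defect in the censoring rule. As written, an unanswered AF item with no positive record elsewhere is analysed as freedom from AF at day 351, and the error can only raise the success rate.

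Its size is unknown. Under equal recurrence risk, f × (1 − S) is close to an upper bound: 0.3 to 2.6 points at S = 74% for f from 1 to 10%, and less where earlier visits recorded AF status. If patients with blank answers recur more often than the rest, the overstatement would be larger for a given f. A reader might infer that the reported rate will be materially inflated. The documents do not support that, because they do not show how often the item is blank, and f may be near zero.

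One further limit: the annotated eCRF (SAP Appendix E) is not in the text I worked from, so I cannot tell whether the AF item is a yes/no field or a tick-box.

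**What to change.** In SAP 8.1.2, for patients without a reported recurrence, replace the last study contact by the date of the last contact at which AF status was recorded, and no later than the date of death. Keep every recorded recurrence as an event, whatever its source. If the AF item proves to be a tick-box, the SAP must also state which entries count as recording AF status. Report the number of 12-month forms without an AF answer; this fits within the missing-data analysis already listed in Appendix D.

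Leave FAS membership in SAP 4.3 and the visit-count definition in 6.1 unchanged. Making an answered AF item, or being alive, a condition of a valid form could remove a patient with a true earlier recurrence from the FAS, take that event out of the estimate, and itself raise the success rate.

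The cost is one sentence and one derivation. The objective does not change, so under CIP 4.4 the SAP can carry the departure from CIP 4.4.1, with its justification, without an amendment. Some patients are censored earlier, so the interval is slightly wider and the success rate may be slightly lower. If no forms are blank and no censoring date falls after death, the result does not change.

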## 4.4 Extended Full Analysis Set

The *Extended Full Analysis Set* (EFAS) consists of all patients of the FAS and thereof patients without documented AF re-ablation (each ablation technology i.e. additional GOLD-AF procedure) until the 12MFU (<351d after the first documented procedure). Also, only patients with a successful first documented procedure (by PVI confirmation) will be member of the EFAS. This population will be used to evaluate the effect of the first documented procedure, in a clearer way.

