### 4.2 Baseline Analysis Set

The *Baseline Analysis Set* (BAS) consists of all patients of the APS and patients:

- where baseline signature has been taken (signed eCRF)
- with AF who are scheduled for Phased RFA
- that meet all remaining eligibility criteria
- provide any further documentation at baseline
- a phased RFA procedure was started - procedure form was fulfilled at least: date of the procedure, PVAC GOLD catheter used (opened), number of PV applications > 0
- patient did not exit the study prematurely for the reason: Patient were enrolled, but Phased RFA procedure was not started

According to the Appendix B, the BAS will be used for the interim and final analysis as well as for post-hoc analysis. The final analysis includes the additional objective (SAP chapter 8.2) and ancillary objectives (SAP chapter 8.3), where the BAS will be applied.

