## 5 For analysis, the EFAS will be used in the same way as the FAS. Protocol Violations

In this registry, the analysis is limited to patients with signed patient informed consent and complete date of patient informed consent (otherwise no further entry in the eCRF was possible) who are scheduled for Phased RFA for AF catheter ablation treatment. Furthermore, the patients have to fulfil the eligibility criteria of an age  $\geq 18$  years as well as a signed PIC/PDRF which allows the analysis of collected personal data during the participation in the registry (up to 14 months after the initial Phased RFA procedure). CRF forms documented 14 months after procedure (440 days) will be ignored for analysis.

In this registry it is not distinguished between a broader full analysis set and a more compliant per-protocol set that excludes all major violators. Therefore, the definition of major violators is not applicable.

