## 8.1 Statistical analyses for the main objective

### 8.1.1 Estimate Phased RFA 12 month success rate

Success rate estimated as the time to first AF re-occurrence event from the first documented procedure. Data about AF events will be collected since the first documented procedure, including 90 days of the "blanking period" and closes at 12 months FU. If no AF events occur during the follow-up period (considering the "blanking period") up to 12 (+2) months, the case is considered to be "event-free". Calculations will be done for exact 12 months (351 days) after first documented procedure.

Main objective will be calculated for the BAS, FAS and EFAS (see chapter 4 and Appendix B). A successful first documented procedure (successfulness by PVI confirmation) is the basis to calculate the main objective. Patients with a procedure during the "blanking

---

 in the service agreement #2 refers to the final report, which is one and the same document for this study

period" of 90 days after first documented procedure will be excluded from main objective calculations.

Predefined AF re-occurrence definition from CIP Version 2.0 will not be applied to calculate the main objective. Further analysis might be used to estimate Phased RFA success rate considering (re-)occurring left Afl events.

AF re-occurrence event defined as:

- AF pharmacological and/or electrical CV
- AF more the 30 sec on ECG/EGM
- AF less than 30 sec in combination with AF symptoms
- Re-ablations for AF

For this analysis adjudicated AE data and coded AE data (free text fields) will be used. AF re-occurrence event rate will be estimated with and without the use of antiarrhythmic drugs at time of the 12 month follow-up. AF re-occurrence rates will be calculated for patients from BAS and FAS (Appendix B) which need to have a signed 12 month FU / 12 month FU by phone form by definition. AF re-occurrence is defined as the first event of AF re-occurrence event and their related date information based on the following eCRF forms and data fields:

**Table 4:** Main objective variables at 12MFU / General FU form

eCRF field	Related date field	Related FID's annotated eCRF (V1.3, V1.4)
Reason for visit: AF re-occurrence	Date of visit	F11000050 F11000010
Re-ablation reason: Due to AF- occurrence	Date of visit	F11000070 F11000010
History of arrhythmias since last visit: AF	Date of first occur- rence	F12000012 F12000050

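### The EFAS 12-month success rate leaves out patients who had an endpoint event (AF re-ablation), and the SAP gives no single rule for AF redos within 90 days

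*SAP*

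**What the plan says.** **Analysis sets.** SAP 4.4 builds the EFAS from "all patients of the FAS and thereof patients without documented AF re-ablation", by any technology, before day 351, and also requires a first procedure confirmed successful by PVI. The sentence that has run into the heading of SAP section 5 adds that "the EFAS will be used in the same way as the FAS". SAP 4.3 assigns the main objective to the FAS. SAP 4.2 names other objectives for the BAS: "The final analysis includes the additional objective (SAP chapter 8.2) and ancillary objectives (SAP chapter 8.3), where the BAS will be applied". SAP 8.1.1 then states: "Main objective will be calculated for the BAS, FAS and EFAS". Table 13 and Appendix B list the same three sets, and none of these places ranks them.

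**Endpoint.** The event list in SAP 8.1.1 includes "Re-ablations for AF". The time point is fixed: "Calculations will be done for exact 12 months (351 days) after first documented procedure".

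**Redos within 90 days.** Three instructions apply:
- SAP 8.1.1: patients with a procedure in the blanking period "of 90 days after first documented procedure will be excluded from main objective calculations".
- SAP 8.1.2, blanking sentence: an AF re-occurrence event in that period is not considered.
- SAP 8.1.2, later sentence: a patient with an additional procedure, whenever it takes place, stops being event-free at the first such procedure.

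Protocol 4.4.1 lists re-ablation for AF as an endpoint and has neither the EFAS restriction nor the early-procedure exclusion.

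**The concern.** The 12-month success rate is the registry's one main objective. A set defined by the absence of re-ablation over the window in which re-ablation counts as failure is selected on the outcome. No re-ablation before day 351 can appear as a failure in it, so its rate answers a conditional question. The SAP nevertheless presents it as one of three unranked answers to the main objective.

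The early-redo wording matters for the other two sets. Programmers following the text could remove, ignore or count the same patient. The form used may also decide the result. Protocol 7.2 requires no Procedure form for a redo with another technology and sends it to the General FU form. A Phased RFA redo could therefore be read as an additional procedure, and a redo on the same day with another technology as a blanked event. The blanking sentence also cites Tables 5, 6 and 7, whereas the main-objective variables are in Tables 4, 5 and 6. Table 4 holds the General FU re-ablation fields, and Table 7 holds safety variables.

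**Working it through.** The documents give no figure for the effect of the EFAS or of the early-redo rules, so there is none to reproduce. The SAP's planned precision of ±3.8% is not used as a yardstick, because it does not follow from its own inputs: 1.96 × √(1.2 × 0.20 × 0.80 / 800) = 0.0304, or ±3.0%.

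**Inputs**
- S = 0.74: success with all AF re-ablations counted as events. The value is the one Protocol 4.4.1 cites for the predecessor catheter at about 10 months, used here as an illustration.
- r: share re-ablated for AF before day 351. Assumed 2%, 5%, 10%.
- d: share with an AF redo within 90 days. Assumed 1%, 3%, 5%.
- Complete follow-up. The EFAS requirement of a successful first procedure is left out of the arithmetic.

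**EFAS.** Every re-ablated patient is a failure, so removal takes r from the denominator and nothing from the numerator. EFAS rate = S/(1 − r):
- r = 2%: 0.74/0.98 = 75.5%
- r = 5%: 0.74/0.95 = 77.9%
- r = 10%: 0.74/0.90 = 82.2%

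If the 8.1.1 exclusion already removes early redos from the FAS, the EFAS–FAS gap is S/(1 − r) − S/(1 − d):
- r = 2%, d = 1%: 0.8 points
- r = 5%, d = 1%: 3.1 points
- r = 5%, d = 3%: 1.6 points
- r = 10%, d = 3%: 5.9 points
- r = 10%, d = 5%: 4.3 points

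**Early redos** (BAS and FAS only, since the EFAS drops these patients anyway). Counted = S. Excluded = S/(1 − d). Ignored = S + d × g, where g is the share with no later event.

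| d | Counted | Excluded | Ignored, g = 0.5 | Ignored, g = 1 |
|---|---|---|---|---|
| 1% | 74.0% | 74.7% | 74.5% | 75.0% |
| 3% | 74.0% | 76.3% | 75.5% | 77.0% |
| 5% | 74.0% | 77.9% | 76.5% | 79.0% |

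The largest spread between rules is 1, 3 and 5 points.

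**Direction under censoring.** Take 800 patients, of whom 40 have early redos and all 40 recur at day 340. The other 760 have no event, and 200 of them are censored after day 90 and before day 340. Counting the redos gives 760/800 = 95.0%. Ignoring them leaves 600 at risk at day 340, and Kaplan-Meier gives 1 − 40/600 = 93.3%. In a set with censoring, such as the BAS, ignoring early redos can therefore also lower the estimate.

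**The case against.** The registry is descriptive and tests no hypothesis. SAP 4.3 points to the FAS for the main objective, and 8.1.2 runs the subgroup Cox models in FAS patients. BAS and FAS rates will stand beside the EFAS rate, and 4.4 states the narrower purpose of showing the effect of the first procedure more clearly. Much of this stands: later redos remain failures in the BAS and FAS, and recurrences without re-ablation still count in the EFAS. But the estimate is itself the deliverable, and a redo for AF is a listed failure of the first procedure. The stated purpose therefore does not justify removing it and then using the set like the FAS.

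The early-redo rules also have a coherent sequential reading. First 8.1.1 removes patients with a procedure within 90 days. Then 8.1.2 blanks AF events in those who remain, and its later sentence says mainly that blanking does not restart. This is possible, so a reader should not infer an unavoidable contradiction. However, the SAP does not state this order, and the absence of any time limit in the later sentence speaks against it.

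Three further inferences go beyond the documents:
- *Acute failures are excluded throughout.* SAP 8.1.1 calls a successful first procedure the basis of the calculation. This may only name the reference procedure, as SAP section 7 does for time calculations.
- *The Appendix C subgroup of non-successful first procedures must be empty in the EFAS.* That depends on the definition. SAP 4.4 uses PVI confirmation, SAP 8.3.1 uses a composite that also requires PVAC catheters only, and Protocol Appendix 1 relies on the operator's judgement.
- *Every additional procedure is an AF event.* Protocol Appendix 1 separates a repeated attempt after an unsuccessful index procedure from a re-ablation for recurrence. SAP 8.2.2 lists left Afl as a separate reason for ablation, and 8.1.1 leaves left Afl out of the endpoint.

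**Conclusion.** The point holds in two parts. First, the EFAS success rate is inflated by construction, by the factor 1/(1 − r): from 74% to 77.9% at 5% re-ablated and to 82.2% at 10%. This rests on complete follow-up, on re-ablations otherwise counting as events, and on assumed shares. The difference from the reported FAS rate is smaller if early redos are excluded there. Combining the 20% re-ablation assumption of SAP 3.3 with 74% would give 0.74/0.80 = 92.5%. A reader might take that as the expected EFAS result, but the two figures come from different sources and the documents do not present them as a joint scenario.

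Second, AF redos within 90 days have three possible treatments and no order of precedence. At assumed shares of 1% to 5%, the treatments differ by up to about 1 to 5 points. With complete follow-up, excluding or ignoring these patients cannot lower the rate compared with counting them. A reader might extend that to every set, but the example above shows that ignoring them can move a censored BAS estimate either way.

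Whether acute success is an inclusion condition needs clarifying; it is not a demonstrated exclusion.

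**What to change.** In the SAP:
- Remove the EFAS from the main objective in 8.1.1, Table 13 and Appendix B, or label it exploratory and conditional on no re-ablation. Delete the sentence stating that "the EFAS will be used in the same way as the FAS".
- Confirm in 8.1.1 that the FAS is the headline set, as 4.3 indicates, with the BAS as supportive.
- State one early-redo rule. Delete the 8.1.1 exclusion. Count a re-ablation for AF, by any technology and on whichever form it is recorded, as an event at its date, as an explicit exception to blanking. Keep the exclusion rule as a sensitivity analysis.
- Limit that rule to re-ablation for AF. State separately how the analysis handles repeated attempts after an unsuccessful index procedure and ablations for left Afl, which the additional-procedure sentence in 8.1.2 mixes together.
- Correct the table reference in 8.1.2 to Tables 4, 5 and 6.
- State whether acute success is an inclusion condition for the headline set, and which success definition the Appendix C subgroup uses.

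The cost is SAP wording only, with no new data. The reported success rate may be less favourable.
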